7.7 Quality control

7.7.1 Data quality management

Novartis data management or a designated CRO will ensure that database quality processes are followed including review of the data entered into the CRFs by site staff for completeness and accuracy, and in accordance with the data validation plan. Once data are entered into the eCRFs and if the site subsequently edits the data, the database contains an audit trail to track the updates. Details may be found in the Data Handling Plan.

7.7.2 Data recording and document retention

In all scenarios, the physician must maintain source documents for each patient in the study, consisting of case and visit notes (hospital or clinic medical records) containing demographic and medical information, and the results of any other tests or assessments. All information entered in the CRF must be traceable to these source documents in the patient's file.

The physician must give Novartis (or designee) access to all relevant source documents to confirm their consistency with the CRF entries. No information in source documents about the identity of the patients will be disclosed.

7.7.3 Site monitoring

Formal site monitoring will be performed as described in the Monitoring Plan for this study.

Novartis Data Management or a designated CRO will assure compliance monitoring.

7.8 Limitations of the research methods

The absence of randomization and of a control group in this single arm study is not able to account for selection bias. The observational nature of the study, without using standardized assessment procedures, is also not able to account for potential information bias.

Nonetheless, this study design will be able to describe what is observed when voretigene neparvovec is used in the real-world setting, when patients are treated as per the current standard of care.

Observational studies are prone to missing data, particularly when data is collected retrospectively. Therefore, retrospective data collection is limited to patients who were treated prior to the start of the registry study.

No formal statistical evaluations are planned. Output will be limited to data listings and descriptive statistics, where applicable.

7.9 Other aspects

None applicable.

8 Protection of Human Patient

Confidentiality

Medical records with protected health information (PHI) will be kept separately from study records at each study site. Study patients will be assigned unique patient identifiers to protect confidentiality. De-identified patient data will be entered into eCRFs. All data and records generated during this study will be kept confidential and in accordance with local regulations, institutional policies, and European data protection law (e.g., General Data Protection Regulation (GDPR)). The study site personnel will not use such data and records for any purpose other than conducting this study.

Risk assessment

As this is a minimal risk study, the chief risk is loss of confidentiality. All study personnel with access to the patient's medical records/source documents will be trained on the applicable requirements for maintaining a patient's confidentiality. There is also the potential risk of discomfort from ophthalmic examinations.

Regulatory and ethical compliance

Compliance with Novartis and regulatory standards provides assurance that the rights, safety, and well-being of patients participating in non-interventional studies are protected (consistent with the principles that have their origin in the Declaration of Helsinki) and that the study data are credible and responsibly reported.

This study was designed and shall be implemented and reported in accordance with the Guidelines for Good Pharmacoepidemiology Practices (GPP) of the International Society for Pharmacoepidemiology (ISPE 2016), the STROBE (Strengthening the Reporting of Observational Studies in Epidemiology) guidelines ([Vandenbroucke et al 2007](#)), and with the ethical principles laid down in the Declaration of Helsinki.

This study is fulfilling the criteria of a 'European Network of Centres for Pharmacoepidemiology and Pharmacovigilance (ENCePP) study' and follows the 'ENCePP Code of Conduct' (European Medicines Agency 2010).

Informed consent procedures

The physician must keep the original signed informed consent/assent form signed by the patient or parent/guardian (a copy of the signed form is given to the patient).

Eligible patients may only be included in the study after providing written (witnessed, where required by law or regulation), IRB/EC-approved informed consent, or, if incapable of doing so, after such consent has been provided by a legally acceptable representative of the patient. In cases where the patient's representative gives consent, the patient should be informed about the study to the extent possible given his/her understanding. If the patient is capable of doing

so, he/she should assent by personally signing and dating the written informed consent document or a separate assent form. Because this is a long-term study, the investigator should check the progressing maturation of pediatric patients and their ability for assent. When an adolescent is legally emancipated, i.e. ceases to be a minor as defined in national law, informed consent must be sought directly from the individual and as soon as possible.

Informed consent must be obtained before any data are collected. The process of obtaining informed consent and assent should be documented in the patient source documents.

Novartis will provide to treating physicians or other involved medical professionals in a separate document a proposed informed consent form that complies with the Declaration of Helsinki principle and regulatory requirements and is considered appropriate for this study.

9 Management and Reporting of Adverse Events

All adverse events (AE) will be collected and recorded in the study database, irrespective of seriousness or causal association. All **serious adverse events (SAEs)** and reports of drug exposure during **pregnancy** that occurred in patients exposed to the Novartis drug(s) of interest, irrespective of causality, will be reported to Novartis Patient Safety within 24 hours of becoming aware of the event. All **non-serious AEs** and events describing a special scenario will be recorded in the study database within 10 calendar days of site awareness and reported to Novartis Patient Safety on a periodic basis via batch reports.

Adverse Drug Reactions (ADRs) occurring in patients exposed to a Novartis drug other than the Novartis drug of interest (i.e., voretigene neparvovec), can be reported to the local Health Authority in accordance with national regulatory requirements for individual case safety reporting or to Novartis Patient Safety as a spontaneous report. All adverse reactions identified for non-Novartis products should be reported to the local Health Authority in accordance with national regulatory requirements for individual case safety reporting or the Marketing Authorization Holder as these will not be recorded in the Novartis safety database. All study site staff and physicians who follow patients will be trained on voretigene neparvovec safety reporting procedures and regulations as outlined below.

9.1 Adverse event collection and reporting

Definition of AE

An **adverse event (AE)** is any untoward medical occurrence in a patient administered a medicinal product and which does not necessarily have a causal relationship with this treatment. An AE can therefore be any unfavorable and unintended sign (including an abnormal laboratory finding), symptom, or disease temporally associated with the use of a medicinal product, whether or not considered related to the medicinal product.

A **serious adverse event (SAE)** is defined as an AE which:

- Results in death or is life-threatening
- Results in persistent or significant disability/incapacity
- Constitutes a congenital anomaly/birth defect
- Requires inpatient hospitalization or prolongation of existing hospitalization, unless hospitalization is for:

- Routine treatment or monitoring of the studied indication, not associated with any deterioration in condition. This would include when the patient is hospitalized either pre or post-injection for routine monitoring, as per local custom.
- Elective or pre-planned treatment for a pre-existing condition that is unrelated to the indication under study and has not worsened since the start of the drug of interest
- Social reasons and respite care in the absence of any deterioration in the patient's general condition
- Is medically significant, i.e., defined as an event that jeopardizes the patient or may require medical or surgical intervention to prevent one of the outcomes listed above e.g. may require treatment on an emergency outpatient basis for an event not fulfilling any of the definitions of a SAE given above and not resulting in hospital admission

Note: Transmission of infectious disease via medication is considered to be a serious adverse reaction and should be reported and assessed as medically significant in the absence of other seriousness criteria.

An **adverse drug reaction** (ADR) is a response to a medicinal product which is noxious and unintended. An ADR implies at least a reasonable possibility of a causal relationship between a medicinal product and an adverse event.

The **Novartis drug of interest** evaluated in this study is voretigene neparvovec.

AE Collection

All AEs from all patients enrolled in the study must be collected and recorded in the study database, irrespective of seriousness or causal association. For patients who have been dosed prior to the enrollment in the registry, all the AEs from the time of dosing upto the time of entry to the registry should also be collected and recorded in the registry database.

The occurrence of AEs should be sought by non-directive questioning of the patient at each visit during the study. AEs may also be detected when they are volunteered by the patient during or between visits or through physical examination, laboratory test, or other assessments. Medical conditions/ diseases ongoing before starting treatment with a study drug are only considered AEs if they worsen after receiving the Novartis drug of interest.

All AEs must be recorded on the AE case report form (CRF) with the following information:

1. the severity grade (mild, moderate, severe)
2. the site (right eye, left eye, both eyes, or non-ocular)
3. its relationship to the voretigene neparvovec (vector and/or transgene), the subretinal injection procedure, the concomitant use of corticosteroids that are administered as part of the treatment, a combination of these procedures and products (suspected/not suspected)
4. its duration (start and end dates or if continuing at final exam)
5. whether it constitutes a SAE

In addition, all reports of the following **special scenarios**, whether or not associated with AEs, are also collected and reported in the same manner as AEs:

- Drug-drug or drug-food interaction
- Drug use during lactation
- Lack of efficacy

- Overdose
- Intentional drug abuse and misuse
- Medication errors including drug maladministration
- Dispensing or prescribing errors
- Drug dependence or addiction
- Withdrawal reaction/ syndrome or rebound symptoms
- Unexpected beneficial effect
- Treatment non-compliance (with clinical symptoms)

A standardized safety questionnaire ([Section 12.1](#)) will be used, in conjunction with clinical observations and ophthalmic examination results, to solicit **Adverse events of special interest (AESI)** information. At each visit the patient should be specifically questioned on each of these AESIs. The AESI will be captured on the AE case report form (CRF).

The following events are designated AESIs:

- Ocular AEs
- Lack of efficacy and/or decline in efficacy over time
- Third-party transmission
- Host immune response
- Development or exacerbation of oncologic, hematologic, neurologic, or auto-immune diseases

Note: In addition to the reporting laid out above, any occupational or accidental exposure, for example of study personnel or family members of the patient should be reported to the local Health Authority in accordance with national regulatory requirements for individual case safety reporting or to Novartis Patient Safety as a spontaneous report.

Any action taken with study drug or addition of treatment medication as a result of an AE should be recorded on the AE eCRF. Some examples to be recorded are: no action taken (i.e., further observation only) or not applicable/unknown; study drug dosage increased/reduced/not changed/ interrupted; study drug withdrawn due to this AE.

Once an AE is detected, it should be followed until its resolution or until it is judged to be permanent, and assessment should be made at each visit (or more frequently, if necessary) of any changes in severity, the suspected relationship to the study drug, the interventions required to treat it, and the outcome.

Information about common adverse effects already known about the study drug(s) can be found in the locally available labeling document for the approved indication under evaluation in this study.

AE Reporting

Serious adverse events (SAE)

Information about **all treatment-emergent SAEs that occur after enrollment** into the registry study, irrespective of causality, must be recorded in the Novartis safety database. The treating physician or other involved HCP must assess the relationship to the Novartis drug, complete the AE Report Form and send the completed, signed form by fax/ email immediately without

undue delay, but under no circumstances later than **within 24 hours of obtaining knowledge of the events (Note: if more stringent, local regulations regarding reporting timelines prevail)** to the local Novartis Patient Safety department.

The investigator is responsible for reporting any SAEs prior to entry into this registry to their local Health Authority according to local regulations. Therefore, **all treatment-emergent SAEs that have occurred prior to a patient's enrollment** into the registry study should have been reported previously to the local Health Authority by the investigator as per local regulations. These SAEs that occurred before entry to the registry must be recorded as SAEs in the CRF, but are not required to be additionally reported to the local Novartis Patient Safety department.

The email address, telephone and telefax number of the contact persons in the local Patient Safety department, specific to the site, are listed in the treating physician/ HCP folder provided to each site. The original copy of the AE Report Form and the fax confirmation sheet or the email must be kept with the CRF documentation at the study site.

Exposure during pregnancy of study patient and pregnancies in partners of patient treated with voretigene neparvovec

Any occurrence of a pregnancy in a patient exposed to the Novartis drug(s) of interest after enrollment into the registry study must be recorded on the CRF and reported to Novartis **within 24 hours** of learning of its occurrence. The pregnancy should be followed-up to determine the outcome, including spontaneous or voluntary termination, details of the birth, and the presence or absence of any birth defects, congenital abnormalities, or maternal and/or newborn complications. Standard Novartis Safety follow-ups are conducted for reports of pregnancy and data on health of newborns are collected for one year after delivery.

Information about the pregnancy should be recorded on the respective CRF as well as on the Pregnancy Form and reported by the treating physician or other involved HCP to the local Novartis Patient Safety department. In case of any congenital abnormality, birth defect or maternal and newborn complications, the possible relationship to the Novartis drug should be reported. Information on whether the baby was breast fed should be included where appropriate.

For patients who have been dosed prior to the enrollment in the registry, any pregnancies occurring between the time of dosing and entry to the study should be collected and recorded on the respective CRF. Such pregnancies do not need to be additionally reported to Novartis Patient Safety.

Additionally, any SAE/ non-serious AE experienced during pregnancy must be collected on the respective CRF and reported to Novartis following the respective reporting routes described in this section.

Pregnancy outcomes must be collected for the female partners of any males who took the Novartis drug(s) of interest in this study. Consent to report information regarding these pregnancy outcomes should be obtained from the female partner.

Non-serious AEs and events describing a special scenario (other than drug exposure during pregnancy)

Information on all non-serious AEs and events describing a special scenario must be collected on the individual patient eCRFs **within 10 calendar days** of the site becoming aware of it.

Information on all non-serious AEs that occurred in patients exposed to the Novartis drug(s) of interest is then transferred from the study database to the Novartis Patient Safety department by Novartis data management group on a periodic basis as per the terms defined in the Data Handling Plan (DHP).

Protocol-exempt events

The following events are defined as “exempt” from collection and entry into the clinical and safety database.

- Any clinically significant abnormal laboratory findings or other abnormal safety assessments which are associated with the underlying disease, unless judged by the study site physician to be more severe than expected for the patient’s condition.
- All reports of lack of efficacy and/or decline in efficacy over time should be reported as AESIs. However the disease/disorder being studied, or expected progression, signs, or symptoms of the disease/disorder being studied, **unless more severe than expected for the patient’s condition** (e.g., expected changes in the fundus appearance consistent with the underlying disease and without any associated visual function changes) is not required to be reported as an AE.

Any protocol-exempted event which is suspected to be related to voretigene neparvovec (i.e., an Adverse Drug Reaction, ADR) should be reported by the investigator to Novartis Patient Safety as a spontaneous report or to the local Health Authority in accordance with national regulatory requirements for individual case safety reporting.

Safety reporting for Novartis drugs other than the Novartis drug(s) of interest and for non-Novartis drugs

Adverse Drug Reactions (ADRs) occurring in patients exposed to a Novartis drug other than the Novartis drug of interest (i.e., voretigene neparvovec), can be reported to the local Health Authority in accordance with national regulatory requirements for individual case safety reporting **or** to Novartis Patient Safety as a spontaneous report.

All adverse reactions identified for non-Novartis drugs should be reported to the local Health Authority in accordance with national regulatory requirements for individual case safety reporting or the Marketing Authorization Holder as these will not be recorded in the Novartis safety database.

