7.4 Study size

This study is intended to collect long-term safety follow-up information and the sample size estimate is not based on statistical measures. Every effort will be made to enroll all patients treated with voretigene neparovec, and it is expected that a minimum of 40 adult or pediatric patients can be enrolled over a five-year enrollment period.

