7.6 Data analysis

This study is intended to descriptively document the frequency and severity of events of interest related to voretigene neparovec (vector and/or transgene), the subretinal injection procedure, the concomitant use of corticosteroids, or a combination of these procedures and products. The Full Analysis Set (FAS), defined as all individuals for whom an informed consent/assent was signed and who are enrolled in the study and received at least one injection of voretigene neparovec, will be used to summarize all data.

Continuous variables will be summarized in terms of mean, standard deviation, median, minimum and maximum. Other descriptive statistics (e.g., quartiles, coefficient of variation) may be reported when appropriate. Categorical variables will be summarized using frequency

counts and percentages. Unless otherwise noted, the denominator for the percentages will include all patients in the FAS population.

The unit of analysis for disposition, demographics and baseline diagnoses will be patient; the unit of analysis for ophthalmic examination findings will be right eye and/or left eye. The unit for non-ocular AEs will be patient; the unit for ocular AEs will be eye(s). The unit for other variables will be patient or eye(s) as appropriate.

Analyses to assess the impact of subgrouping based on selected variables which become of interest during the study will be performed as defined in the Statistical Analysis Plan (SAP).

Interim data assessments will occur at a minimum, on an annual basis and will be included in annual progress reports. A complete description of the statistical analyses and methods will be available in the SAP.

7.6.1 Demographics, baseline disease characteristics, disposition, ophthalmic examination findings, and other variables

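### Section 9.1 lets exempt events suspected to be product-related bypass the AE CRF, and possibly the sponsor, so some suspected ADRs may be missing from the by-relationship tables

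*Protocol*

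**What the plan says.** Under the protocol-exempt events heading, Section 9.1 removes two classes of event "from collection and entry into the clinical and safety database":

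- clinically significant abnormal laboratory or other safety findings associated with the underlying disease, "unless judged by the study site physician to be more severe than expected" for that patient;
- the disease under study and its expected progression, signs or symptoms, again unless worse than expected. The same bullet keeps efficacy failures in: "All reports of lack of efficacy and/or decline in efficacy over time should be reported as AESIs".

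The closing paragraph deals with exempt events that the investigator thinks the product may have caused: "Any protocol-exempted event which is suspected to be related to voretigene neparvovec (i.e., an Adverse Drug Reaction, ADR) should be reported". On the route, it says that they "should be reported by the investigator to Novartis Patient Safety as a spontaneous report or to the local Health Authority", following national rules.

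The general rule that opens Section 9 is different: "All adverse events (AE) will be collected and recorded in the study database, irrespective of seriousness or causal association". Section 9.1 repeats it under AE collection and makes the AE CRF the place where severity, eye and suspected relationship are recorded. The purpose given in Section 7.6 is to "descriptively document the frequency and severity of events of interest related to" the product, the subretinal injection procedure, the corticosteroids or a combination. Section 7.6.2 tabulates AEs by relationship as appropriate.

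**The concern.** A suspected causal link is a reason to bring an event into a safety registry. In the closing paragraph of the exemption it instead triggers a route that runs outside the CRF. Read literally, an AE with no suspected link to treatment must be entered, while an exempt event already judged a suspected ADR need not be. Section 9.1 offers the same two-way route, spontaneous report or health authority, for ADRs of the sponsor's other drugs, which are not under study.

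What is at stake is the by-relationship AE table, which bears directly on the primary objective of collecting all AESIs, AEs and SAEs (Section 6.1). The overlap with a current risk adds weight. The second exempt class is illustrated by expected fundus changes without change in visual function, while version 02 added chorioretinal atrophy to the safety questionnaire, and Section 5 lists vision loss due to progressive chorioretinal atrophy as an important potential risk. A site that sees a fundus change and suspects the product meets one rule that requires entry and another that waives it.

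**Working it through.** The protocol gives no figure to reproduce; its study size is not derived ("the sample size estimate is not based on statistical measures"). The check is to follow one event through the rules.

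**Step 1: which events are affected.** The event must be (a) associated with the disease or part of its expected course, (b) no more severe than expected, (c) not a lack or decline of efficacy, and (d) still suspected to be related to the product. Exempt status depends on (a) to (c). Causality plays no part in it, so (d) does not end the exemption.

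**Step 2: where such an event can go.**

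| Route taken by the site | AE CRF | Sponsor's safety database | Report summaries |
|---|---|---|---|
| Health authority only | No path given | No path given | No path given |
| Spontaneous report to the sponsor | No path given | Yes | Possibly, through the safety-database wording in 7.6.2 |
| Also a Yes on the safety questionnaire, or classed as an ocular AESI | Required by Section 9.1 and Annex 12.1, waived by the exemption | By the usual AE route, if entered | Yes, if entered |

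**Step 3: the rules that conflict with the closing paragraph.**

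- Section 9 and Section 9.1 (AE collection): every AE goes into the study database whatever its suspected cause.
- Section 9.1 (SAE reporting): every treatment-emergent SAE after enrollment goes to the sponsor within 24 hours. The exemption makes no exception for serious events.
- Section 9.3: every AESI, AE and SAE after consent must be reported to the sponsor's patient safety department. A report to the health authority alone does not meet this.
- Annex 12.1: any Yes, including chorioretinal atrophy or another ocular event, must be reported as an AE or SAE and documented in the eCRF.

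The closing paragraph also names only the product. An exempt event suspected to be due to the injection procedure or the corticosteroids has no reporting route there at all, although the AE CRF and Section 7.6 cover all three causes.

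**Step 4: effect on the tables.** Section 7.6 uses all FAS patients as the default denominator. An omitted event leaves the numerator and not the denominator, so any error in related-AE incidence is downward. Per patient at the stated minimum of 40:

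1/40 = 0.025 = 2.5 percentage points,

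provided that the patient has no other recorded event in the same table row. More than 40 patients makes the step smaller. For ocular AEs counted by eye (Section 7.6), 40 patients contribute 40 to 80 treated eyes, so one eye is 1/80 = 1.25 to 1/40 = 2.5 points. The protocol gives no number of affected patients by which to multiply these steps.

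**The case against.** The strongest reply is that the exemption is an explicit exception to a general rule, of a kind that the ENCePP checklist (item 3.5) itself envisages, and that its closing paragraph adds a reporting duty without forbidding CRF entry. The class is small. It needs an event that looks like the disease, is no worse than expected and is still blamed on the product, and efficacy failures stay in as AESIs. All ocular AEs are AESIs, to be captured on the AE CRF, and VA, VF, FST and OCT results are collected whether or not an AE is recorded.

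Much of this stands, and it rules out stronger readings. A reader might infer that these ADRs can never reach the registry tables. That does not follow. Section 7.6.2 says that the report summaries include information from the sponsor's global safety database, although it is unclear whether this covers all AEs or only pregnancies, and Section 9.1 and Annex 12.1 still call for CRF entry of ocular AESIs and questionnaire positives. A reader might also infer that a known share of related events is lost, or that a spontaneous report lacks patient, eye or severity details. The protocol gives no such share and does not describe what a spontaneous report contains.

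What the reply does not remove is the conflict. The other rules require entry and the specific exemption waives it, so a site that omits the event can say that it followed Section 9.1. Nor can the safety-database wording recover a case sent only to the health authority.

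**Conclusion.** The point holds as an inconsistency with a possible downward bias. Section 9.1 allows suspected ADRs among exempt events to bypass the AE CRF and, through the health authority option, the sponsor. This contradicts Sections 9, 9.1 and 9.3 and Annex 12.1. Some suspected ADRs may be missing from the by-relationship tables; the documents do not show that any are. The class is narrow and its size cannot be estimated. The only scale available is 2.5 percentage points per affected patient at 40 patients, which assumes the FAS denominator and no other recorded event for that patient in the row. It deserves correction at the next amendment because it touches the primary objective and is cheap to mend, but it does not put the registry as a whole in doubt.

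**What to change.** Replace the closing paragraph of the protocol-exempt events text with wording to this effect: an event suspected to be related to voretigene neparvovec, the subretinal injection procedure or the corticosteroids is not exempt; it is recorded on the AE CRF and follows the Section 9.1 route for SAEs or non-serious AEs to the sponsor's patient safety department, in addition to any health authority report that national rules require. The health authority report is kept; it just no longer stands in for the study record.

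Tell sites by letter, and ask them to back-enter any such case in an enrolled patient that was reported only by the other routes.

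The cost is one paragraph in the next amendment, one site letter and the back-entered records, whose number is not known from the protocol.
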